The biomarker expression profiles in the PBMC cells can also be detected by the fluorescence-conjugated secondary antibodies. A protocol has been developed to detect the bound antibodies at 680nm and 800nm, by using the DyLight-680 conjugated secondary antibody and the DyLight-800 conjugated antibody (Rockland Antibody), respectively (Figure 9). The images show the bound antibodies for Actin (row 1 and 3), and for GADPH (row 2 and 4) on HTB129 cells, a breast cancer cell, obtained by Odyssey Imaging Systems. Both methods will be used to analyze biomarker expression patterns in the proposed study to identify the more effective method for future experiments.

OMB No. 0925-0001/0002 (Rev. 03/16 Approved Through 10/31/2018) Page	Continuation Format Page Specific Aim 2. Identify those
specific proteins whose expression patterns have changed in	the greatest number of participants after OMT.

28

Sample Size. To estimate the sample size needed to detect a mean difference of 0.5 in ratio of intensity (After/Before) between the OMT and in the control group, standard deviations of intensity (After/Before) in the two groups were estimated using PSL microarray staining, by using the data similar to the images shown in Figure 4. The data integration was carried out for each image by using the ScanAlyze in Image J, the intensity integration programs for DNA and protein microarray analysis. As summarized in Table 2, the mean ratio in the Control group is 1.32 with standard deviation of 0.34 and mean ratio in the Intervention group is 1.42 with standard deviation of 0.32 (28). Those data have been used to calculate the sample size needed for the proposed study as described below.

Group	# Obs	Mean	Std Dev	Median
Control	4	1.32	0.34	1.20
Intervention	6	1.42	0.32	1.43

Table 2 Summary data from PSL Microarray Analysis

Group sample size calculation. Sample size calculations based on the data summarized in Table 2 reveal that recruiting a total 22 participants, 11 in the OMT group and 11 in the control group, will allow us to detect a difference of 0.5 in intensity (After/Before) in the two groups with a power of 0.92 at a significance level of 0.05, using two sample *t*-tests with unequal variances. We propose to use 40 patients for the experiments, 20 in the OMT group, and 20 in the control group. Therefore, we should have an adequately powered study.

Data Extraction and data analysis. The expression profiles of 60 biomarkers in the PBMC samples obtained by the PSL microarray staining, will be extracted by the program ScanAlyze of ImageJ, from the images similar to the above figures. The ratio change of every biomarker protein in PBMC samples, before and after the OMT will be analyzed by DAMAPEP, a software developed at the PI's lab to retrieve, normalize, and scale the data from

the exported intensity integration files. The mean change in intensity (After/Before) of biomarker expression for each of the 60 biomarkers will be compared between the OMT and control group using two sample *t*-test and biomarkers whose expression has changed significantly between the two groups will be identified. If needed, modification on published data analysis protocol and software in the paper (21) will be carried out for the project in order to identify the proteins with statistically meaningful expression change between the OMT group and the control group. The comparison would eliminate and normalize the expression change of biomarkers due to fluctuation and personal variation, and identify those differentially changed biomarkers due to the OMT.

Potential Limitations: The purposed study is investigating the impact of OMT on immune cell biomarkers. OMT can be accomplished with a wide variety of techniques. Most studies investigating the effect of OMT on immune cells use lymphatic pump OMT techniques. Other types of OMT techniques may not have the same effect. The purposed study will use a wide variety of OMT techniques consistent with what a patient with low back pain would receive in a clinical setting and conclude the treatment with a lymphatic pump OMT technique. Therefore, the current design will not allow for conclusions about the effect of any specific type of technique. Future studies will investigate the effect of different types of OMT techniques on the immune cell biomarkers.

Another potential limitation is that the method could be not sensitive enough to detect changes in biomarkers after 30 minutes post OMT. If no changes are seen during the initial investigation we will modify the protocol to increase the sensitivity of the technology or try different OMT techniques.

3. Bibliography and References

- 1. Kuchera ML. Lymphatics approach. In: Chila AG, ed. Foundations of Osteopathic Medicine. 3rd ed. Philadelphia, PA: Lippincott Williams & Wilkins; 2011:786-808.

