Antibody selection and microarray preparation. The goal of this project is to purchase ~60 antibodies, which are the surface biomarkers for different human immune cells. We shall determine the expression patterns of the 60 proteins in the PBMC cells from the participants, before and after the OMT treatment by using the PSL microarray. The proteins with differentially expressed level after the OMT treatment will be identified from data mining and statistical analysis.

We plan to first purchase 30 antibodies, which are the biomarkers for different human lymphocytes. The selected antibodies and their major expression in different lymphocytes are summarized in Table 1. The PSL microarrays containing those antibodies will be made according the design in figure 6 by using the purchased antibodies and the nanoplotter at ATSU, and will be used for the proposed research. Most of the 30 proteins shown in Table 1 are expressed in 1-2 kinds of different lymphocyte cells. An increase or decrease in expression of those proteins could be related to the increase or decrease of the specific types of lymphocytes, which could provide potential mechanism for OMT on immune system activity.

The second set of 30 antibodies will be selected from the \sim 150 surface proteins summarized in the Appendix (with their expression patterns in human immune cells) and purchased later pending the findings from the analysis of the first 30 antibodies. The samples will be saved and stored in liquid nitrogen and retested for the second set of 30 antibodies.

The long-term plan. The long-term plan of the proposal is develop a research methodology for study the effect of OMT on immune system activity. The goal of the current proposal is to generate preliminary data, so that we could apply for the NIH grant to determine the expression patterns of 150-200 cell surface biomarkers for human immune cells in the PBMC cells of the participants, before and after OMT. For this purpose, a grant application based on the preliminary data generated from the current proposal will be submitted to NIH or AOA. Additional antibodies, as those listed in the Appendix, will be purchased if funded. The microarray containing 150-200 antibodies will be made similar to those used in the publication (23), and used for the longterm research.

Table 1. Summary of Antibodies used for the research and their expression in immune cells

B Cells Markers	Myeloid and mast	IK Sell	s	T Cells

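### Sixty separate t-tests with no multiplicity control: at the only stated level, 0.05, about 3 biomarkers are expected to be credited to OMT even if it does nothing

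*Protocol*

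**What the plan says.** Under Data Extraction and data analysis (section 2-4, Specific Aim 2), the protocol sets three things:

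- **The test.** The mean After/Before change in intensity "for each of the 60 biomarkers will be compared between the OMT and control group using two sample" t-tests.
- **The selection rule.** "biomarkers whose expression has changed significantly between the two groups will be identified".
- **The interpretation.** The comparison is said to remove change due to fluctuation and personal variation, and to "identify those differentially changed biomarkers due to the OMT".

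That section gives no significance level and no adjustment. The only level in the document is under Group sample size calculation, where "recruiting a total 22 participants, 11 in the OMT group and 11 in the control group" is said to detect a difference of 0.5 "with a power of 0.92 at a significance level of 0.05". The protocol then plans 20 per arm and concludes that the study is adequately powered.

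Three other passages in section 2-4 bear on the point. The second set of 30 antibodies is to be "purchased later pending the findings from the analysis of the first 30 antibodies". Two detection systems are planned: "Both methods will be used to analyze biomarker expression patterns in the proposed study to identify the more effective method for future experiments". Under The long-term plan, "The goal of the current proposal is to generate preliminary data" for a larger grant application.

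**The concern.** A control arm removes systematic before-to-after change on average. It does not remove chance differences between arms, and with 60 comparisons some of those will pass a single-test threshold. The protocol's claim that the comparison isolates changes due to OMT therefore does not follow from the rule it sets.

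The list of changed proteins is the main product of this analysis and the evidence for the next grant application. The protocol also proposes to read marker changes as changes in particular lymphocyte types and as a possible mechanism. Spurious entries could therefore steer the follow-on study to the wrong cells. Specific Aims promises validation of changed proteins, which could remove some false ones later, but the Approach describes no validation step.

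**Working it through.** **Inputs from the protocol.** 60 biomarkers; level 0.05; difference 0.5 in the After/Before ratio; SD 0.34 (control, 4 observations) and 0.32 (intervention, 6 observations), from Table 2; 11 per arm in the calculation; 20 per arm planned. Sidedness is not stated; two-sided reproduces the protocol's figure.

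**1. The stated power.** Unequal-variance t-test, noncentral t:

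- SE = sqrt(0.34²/11 + 0.32²/11) = 0.1408
- noncentrality = 0.5/0.1408 = 3.55; Welch df = 19.9; critical t = 2.086
- power = 0.9216, against 0.92 stated. The figure is right for one test.

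**2. False positives if OMT does nothing.**

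- Expected number = 60 x 0.05 = 3.0. An expectation adds across tests, so this needs no independence.
- Chance of at least one, if independent = 1 − 0.95^60 = 0.954.

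Markers measured on the same cells are probably correlated. The protocol gives no correlation, so a common value was assumed over a range. Simulation of 60 null Welch tests, 20 per arm, 6000 runs:

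| Assumed correlation | Mean false | Median false | Chance of any, uncorrected | Chance of any, Benjamini-Hochberg 5% |
|---|---|---|---|---|
| 0 | 3.00 | 3 | 0.954 | 0.048 |
| 0.3 | 3.00 | 2 | 0.849 | 0.046 |
| 0.5 | 2.97 | 1 | 0.664 | 0.038 |
| 0.7 | 2.87 | 0 | 0.430 | 0.026 |

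The small departures of the mean from 3 are simulation error.

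**3. Power at the planned 20 per arm.** SE = sqrt(0.34²/20 + 0.32²/20) = 0.1044; noncentrality = 0.5/0.1044 = 4.79; df = 37.9.

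- At 0.05: critical t = 2.025, power 0.997.
- At 0.05/60 = 0.00083: critical t = 3.631, power 0.862.
- For comparison, 11 per arm at 0.05/60 gives 0.391.

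Bonferroni is the strictest of the usual corrections. With 1, 3 or 6 of the 60 markers truly shifted by 0.5 (assumed, independent markers, 3000 runs each), Benjamini-Hochberg power is 0.86, 0.93 and 0.96. At correlation 0.5 it is 0.87, 0.92 and 0.96.

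**4. Sensitivity to the SD.** Pooled pilot SD = sqrt((3 x 0.34² + 5 x 0.32²)/8) = 0.328 on 8 df. Its 95% interval is 0.22 to 0.63 assuming normal data, and its one-sided 80% upper limit is 0.43. Power for a 0.5 difference at 20 per arm, with a common SD assumed in both arms:

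| SD | At 0.05 | At 0.05/60 |
|---|---|---|
| 0.40 | 0.971 | 0.626 |
| 0.43 | 0.948 | 0.527 |
| 0.50 | 0.869 | 0.341 |
| 0.63 | 0.687 | 0.156 |

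**The case against.** **A multiplicity method is commonly left to the SAP, and the analysis section states no level.** Applying 0.05 to each test is indeed an inference from the sample size paragraph. But the protocol is not silent here: it fixes the test, the selection rule and the causal reading, and that reading is unsupported without error control.

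**The protocol allows the published analysis method and software to be modified if needed.** That could admit a correction, and whether the cited method contains one cannot be known from this document. As written, the clause names none and leaves the choice until after the data are seen.

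**This is preliminary screening, with validation promised.** An uncorrected screen is defensible if it is labelled as one. This one is not: its output is described as changes due to OMT. The cited earlier work confirmed its proteins by western blot, but that commits this trial to nothing.

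**Aim 2 is worded as finding proteins that changed in the most participants.** That is a per-participant count, not a comparison of means. The mismatch is real, but the t-test rule is the only selection procedure the analysis section specifies.

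**Correlation makes the headline of 3 look worse than a typical result.** This stands in part. At correlation 0.7 the median is 0 and the chance of any false biomarker is 0.43. The mean stays at 3 because false positives then arrive in clusters.

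**The power after correction is fragile.** This stands. The SDs come from 4 and 6 observations, on data described as similar to Figure 4, whose caption describes flutamide-treated HepG2 cells. The 0.86 should not be printed without its range.

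**Conclusion.** The concern holds. Followed with the only level the protocol states, the rule is expected to credit about 3 of 60 biomarkers to OMT when it has no effect. That expectation assumes 0.05 per test and valid t-tests, and does not depend on correlation. The chance of at least one false biomarker does depend on it: 0.95 if independent, falling to 0.43 at an assumed correlation of 0.7. Benjamini-Hochberg at 5% holds that chance at or below 0.05 in every case tried. On the protocol's own inputs, 20 per arm can bear the correction, though this is uncertain because the pilot SDs are weak. The plan should be changed. The preliminary purpose lessens the severity but does not rescue the attribution to OMT.

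**What to change.** **Data Extraction and data analysis.** State that a biomarker is identified as changed only if it passes Benjamini-Hochberg false discovery rate control at 5% (or Holm) across all biomarkers tested, applied once after both sets of 30 antibodies have been measured. Report uncorrected p < 0.05 results separately as exploratory, not as changes due to OMT. Say that any look at the first 30 serves only to choose the second set.

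**Readout.** Name in advance which detection method supplies the data for this analysis. If both were tested by the same rule there would be 120 tests, and 120 x 0.05 = 6 expected false results under no effect.

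**Group sample size calculation.** Give power for the planned 20 per arm: 0.997 unadjusted and about 0.86 per biomarker at 0.05/60, for a 0.5 difference with SDs 0.34 and 0.32. State that these SDs rest on 4 and 6 observations, and show the fall to 0.63 and 0.53 at an SD of 0.40 and 0.43.

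**Cost.** A few sentences and one line of code, with no added participants. Stated power is lower, and real shifts smaller than 0.5 are more likely to be missed or to appear only in the exploratory list.

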4. PROTECTION OF HUMAN SUBJECTS

4.1 DETAILED DESCRIPTION OF THE PROPOSED INVOLVEMENT OF HUMAN SUBJECTS

The proposed study will involve 40 participants receiving two venous blood draws; one blood draw immediately before and one immediately after the intervention. Twenty participants will receive OMT for up to twenty minutes as part of the protocol with the remaining 20 participants receiving OMT if desired.

4.2 SOURCES OF RESEARCH MATERIAL

a. Demographic information and past medical history. Basic demographic information and past medical history including frequency of low back pain will be collected from participants.

b. Surface protein expression of 60 cell surface proteins in human immune cells, in the peripheral blood mononuclear cells (PBMC) of each participant will be analyzed from peripheral blood before and after intervention.

4.3 RECRUITMENT AND INFORMED CONSENT

Participants will be recruited from the surrounding Kirksville area. A research investigator or their assistant will review the study with a potential participant, determine the participant's eligibility, and obtain informed consent using an informed consent document that will be reviewed and approved by the Institutional Review Board for ATSU-Kirksville pending study funding. The study will be registered with ClinicalTrials.gov.

4.4 POTENTIAL RISKS

4.4.1 PHYSICAL RISKS

The physical risks to the participant include the OMT and venous blood draws. The participant may feel some post-treatment soreness from the OMT and they may experience bruising from the blood draws. 4.4.2 PSYCHOLOGICAL RISKS

There are no psychological risks to the participant from the OMT or blood draws.

4.4.3 SOCIAL RISKS

There are no social risks to the participant from the OMT or blood draws. The health information obtained during the study will be kept in a locked file cabinet and information used in this study will be de-identified prior to data analysis and results dissemination.

4.4.4 ECONOMIC RISKS

There are no economic risks to the participant from the OMT or blood draws.

4.4.5 LEGAL RISKS

There are no legal risks to the participant from the OMT or blood draws.

4.5 ALTERNATIVE PROCEDURES OR THERAPIES

The participant may choose not to participate in the study.

4.6 PROCEDURES FOR PROTECTING AGAINST RISKS

Any residual soreness that a participant experiences from the OMT or blood draws is likely to be insignificant, though the participant may contact the [name] for options regarding care. The results of this research may be published; however, neither participants' names nor identities will be revealed, and records will remain confidential. Confidentiality will be maintained by using coded identification numbers on all forms. All consent forms and study data will be kept and treated as personal medical records. Only the investigators and study personnel will have access to this information. As required by Federal law, all personal health information will be maintained in accordance with the Health Insurance and Portability and Accountability Act (HIPAA) to ensure privacy.

4.7.1 POSSIBLE BENEFITS TO SUBJECT

There are minimal risks to the participants. The minimal risks to the participants are reasonable compared to the knowledge to be gained from the proposed study and the benefit to the osteopathic profession. The participants may benefit from the OMT with regards to their low back pain, though treatment for low back pain is not an intended outcome.

4.7.2 POSSIBLE BENEFITS TO SOCIETY

The benefit to society will be the information obtained regarding the possible effects of OMT on immune biomarker expression. This knowledge can be integrated into the training of future osteopathic physicians.

5. DATA SAFETY MONITORING PLAN

Not applicable.

6 INCLUSION OF WOMEN AND MINORITIES

Women and minorities are encouraged to participate in the proposed study.

7. TARGETED/PLANNED ENROLLMENT TABLE

Time	# patients
Q4, 2017	10
Q2, 2018	30
Total	40

The first set of 10 participants samples will be saved and retested with the second set of 30 antibodies.

8. INCLUSION OF CHILDREN

Children are excluded from this study.

9. VERTEBRATE ANIMALS

Not applicable

10. SELECT AGENT RESEARCH

Not applicable

11. MULTIPLE PD/PI LEADERSHIP PLAN

Not applicable

12. CONSORTIUM/CONTRACTUAL ARRANGEMENTS

Not applicable

13. LETTERS OF SUPPORT (E.G., CONSULTANTS)

[figure not shown]
Not applicable

14. RESOURCE SHARING PLAN

The research findings from this study are expected to be published in JAOA. Travel funds for presentation of the study findings have been requested to attend OMED in 2018.

Program Director/Principal Investigator (Last, First, Middle): [name]

Program Director/Principal Investigator (Last, First, Middle): [name]

39

Appendix

OMB No. 0925-0001/0002 (Rev. 03/16 Approved Through 10/31/2018) Page ____
